6.2.12 Visit 11 - 24 Months Post Visit 2 Follow Up

- Perform focused pulmonary assessment including Vital Signs (heart rate, blood pressure, temperature, respiratory rate, SpO₂) and breath sounds.
- Perform post-bronchodilator spirometry.
- Perform Lung Volumes and DLCO
- Perform 6MWT
- Administer SGRQ
- Administer mMRC
- Review medications and O₂ use.
- Record AEs since last follow-up (See Section 7).
- Discuss maintenance rehabilitation activity plan with Subject.

6.2.13 Visit 12 - 36 Months Post Visit 2 Follow Up

- Perform focused pulmonary assessment including Vital Signs (heart rate, blood pressure, temperature, respiratory rate, SpO₂) and breath sounds.
- Perform post-bronchodilator spirometry.
- Perform Lung Volumes and DLCO
- Perform 6MWT
- Administer SGRQ
- Administer mMRC
- Review medications and O₂ use.
- Record AEs since last follow-up (See Section 7).
- Discuss maintenance rehabilitation activity plan with Subject.

6.2.14 Visit 13 - 48 Months Post Visit 2 Follow Up

- Perform focused pulmonary assessment including Vital Signs (heart rate, blood pressure, temperature, respiratory rate, SpO₂) and breath sounds.
- Perform post-bronchodilator spirometry.
- Perform Lung Volumes and DLCO
- Perform 6MWT
- Administer SGRQ
- Administer mMRC
- Review medications and O₂ use.
- Record AEs since last follow-up (See Section 7).

- Discuss maintenance rehabilitation activity plan with Subject.

6.2.15 Visit 14 - 60 Months Post Visit 2 Follow Up

- Perform focused pulmonary assessment including Vital Signs (heart rate, blood pressure, temperature, respiratory rate, SpO₂) and breath sounds.
- Perform pregnancy test for females of child-bearing potential prior to radiographic procedures.
- Perform post-bronchodilator spirometry.
- Perform Lung Volumes and DLCO
- Perform 6MWT
- Perform SGRQ
- Perform mMRC
- Review medications and O₂ use.
- Record AEs since last follow-up (See Section 7).
- The subject can be exited from the study.

6.2.16 Unscheduled Visits

It is expected that some subjects may present during the follow-up period with complaints (e.g., COPD exacerbation). These visits and the findings should all be recorded on the appropriate eCRFs. Notify the Sponsor if an unscheduled visit occurs.

7 Management of Adverse Events (AEs) and Serious Adverse Events (SAEs)

An adverse event (AE) is any untoward medical occurrence in a study subject. This may include symptom(s), illness, clinically significant abnormal laboratory value or change in value, or worsening in a subject during a clinical study.

It is the responsibility of the investigator to report when he/she becomes aware that an AE has occurred. AE information will be collected throughout the study. Adverse events will be recorded on the eCRF by the investigator or authorized designee. Event/diagnosis, date of onset, severity, duration, and relationship to the procedure/device will be recorded, as well as a detailed description of the Event. All AEs will be followed until they are adequately resolved or stabilized, or for 1 month following study completion or termination, whichever comes first.

Due to the similarity in reported symptoms between an infectious pneumonia and the occurrence of post-Coil implant response (the localized tissue reaction sometimes referred to as "tension induced opacity" and hereafter as Coil Associated Opacity or CAO), the DMC has recommended that Subjects be instructed to immediately contact the PI or authorized designee if the Subject experiences any chest or pleuritic pain/discomfort, fatigue, or increased dyspnea/shortness of breath within approximately two (2) months following each Coil treatment. These symptoms may or may not be accompanied by fever, chills and/or night sweats. Recommendations on diagnosis, treatment and follow-up of these events are provided in the Study Operational Instructions.

Safety data from the various OUS studies that PneumRx has conducted to date have been collected and analyzed. A summary of the safety data is provided in Section 2.4, above.

7.1 Serious Adverse Events

In accordance with 21 CFR Parts 803 and 812, a Serious Adverse Event (SAE) is defined as any untoward medical occurrence that:

1. results in death,
2. is life-threatening,
3. requires inpatient hospitalization or prolongation of existing hospitalization,
4. results in persistent or significant disability/incapacity,
5. is a congenital anomaly/birth defect, or
6. requires intervention to prevent permanent impairment or damage.

In addition, Major Complications, as defined below (which will be adjudicated by the Medical Monitor based on AE/SAE documentation in the eCRFs):

- Death;
- Pneumothorax that requires a chest drainage tube for more than 7 days (from time of chest drainage tube insertion to the time of chest drainage tube removal);
- Hemoptysis requiring an intervention (e.g., blood transfusion(s), arterial embolization, or surgical/endoscopic procedure);
- COPD exacerbation that becomes life-threatening or disabling as a result of an increase in respiratory symptoms requiring in-patient hospitalization of >7 days with or without mechanical ventilation;
- Lower Respiratory Infections (including pneumonia) defined by new or increased clinical symptoms such as fever, chills, productive cough, chest pain, dyspnea or an infiltrate on plain chest x-ray and hospitalization for administration of intravenous antibiotics and/or steroids;
- Respiratory failure defined as a requirement for mechanical ventilatory support (whether via endotracheal tube or mask) for >24 hours; and
- An unanticipated bronchoscopy in order to remove one or more Coils due to a device-related AE. (Note: This definition does not include re-positioning, replacement or removal of the Coil(s) during the procedure.)

All SAEs must be reported to the PneumRx Clinical Affairs immediately (within one working day) using the AE eCRF. To maintain subject confidentiality, the subject shall only be identified by the subject number used on the eCRFs. Further written reports through final resolution of the event, study completion or termination or, in case of permanent impairment, until the event stabilizes and the overall clinical outcome has been ascertained shall be provided to PneumRx, Inc. Clinical Affairs via the eCRF.

7.2 Unanticipated Adverse Device Effect (UADE)

An Unanticipated Adverse Device Effect (UADE) is defined as any serious adverse effect on health or safety or any life-threatening problem or death caused by, or associated with, a device, if that effect, problem, or death was not

previously identified in nature, severity, or degree of incidence in the investigational plan or application (including a supplementary plan or application), or any other unanticipated serious problem associated with a device that relates to the rights, safety, or welfare of subjects.

7.3 Severity of AEs and SAEs

The following general definitions for rating severity should be used for this study:

1. **Mild:** Awareness of signs or symptoms, but easily tolerated and transient; causing no loss of time from normal activities; symptoms may not require medication or a medical treatment; signs and symptoms are transient.
2. **Moderate:** Marked symptoms and discomfort severe enough to cause moderate interference with the subject's usual activities. Symptomatic treatment is possible.
3. **Severe:** Incapacitating with inability to do work or usual activities; signs and symptoms may be of systemic nature or require medical intervention and/or treatment. Hospitalization may be required or prolonged.

7.4 Relationship of an Event

The relationship of an AE or SAE to the underlying disease or to the procedure will be attributed using the following definitions:

1. **Not Related:** There is no evidence that the event has a relationship to the procedure performed.
2. **Possibly Related:** The event has a timely relationship to the procedure performed. However, a potential alternative etiology may be responsible for the adverse event.
3. **Probably Related:** The event has a timely relationship to the study procedure performed and the causative relationship can clearly be established. No potential alternative etiology is apparent.

7.5 Process for Assessment, Recording and Reporting of AEs

Subjects will be instructed at the beginning of the study to report to the investigator any adverse physical or mental changes they experience and they will be asked about adverse events at each visit, including those experienced at the baseline visit prior to, during, or immediately following treatment. All such adverse events reported by the subjects or observed by the investigators will be reported to the Sponsor.

As described in Section 7.0, if the event is deemed to be Serious, such events will be reported to the Sponsor via the completion of the Adverse Event eCRF. The IRB/EC(s) will be informed if the Serious or unexpected adverse event, in the opinion of the Investigator, or the Medical Monitor, is likely to affect the safety of the subjects or the conduct of the study.

An independent DMC will be engaged to provide independent benefit/risk oversight during the conduct of the study. The DMC or a subcommittee dedicated to review of Clinical Events will:

- Review and evaluate Serious Adverse Events on an “as needed” basis and **all** adverse events on a *quarterly basis or on an as needed basis, if the Sponsor requests an unscheduled review.*
- Recommend discontinuation of the study in the event of the occurrence of Serious or Unexpected Adverse Events that are determined by the DMC to pose a significant safety concern.

The DMC will notify the Sponsor, who will in turn notify the FDA or other regulatory bodies, of safety outcome information from the DMC meetings. This information will also be reported as part of required regulatory progress update reports.

7.6 Data Monitoring Committee Composition and Role

An independent DMC will be engaged prior to the enrollment of the first subject. The DMC will be comprised of at least four members, including but not limited to a pulmonary doctor with expertise in COPD, a statistician, a thoracic surgeon, and a Regulatory Affairs Advisor.

The DMC's role will be to review and evaluate safety events and monitor study safety data; and to recommend discontinuation of the study according to the Study Stopping Rules, in Section 8, below.

8 Administrative

8.1 Premature Termination of Study

The clinical study may be terminated at any time in the event of the occurrence of serious or unanticipated AEs that are determined by the DMC to pose a significant safety concern. In addition, the clinical study may be terminated at any time in the event that information indicates that the device will not be commercially viable, or in the event that the sponsor can no longer fund the study.

PneumRx will notify all investigators in the event of a premature withdrawal of IRB/EC approval from any site. The investigators are responsible for informing their IRBs/ECs regarding premature trial termination. Subjects who experienced any SAEs that result in trial termination will be followed to resolution or stabilization.

Study Stopping Rules:

Treatment of subjects will be suspended to allow time for analysis of the safety of the Coil and the LVRC procedure if any of the following are observed:

1. Two or more deaths, as deemed by the Investigator to be possibly or probably related to the Coil device or the LVRC procedure, occur within 30 days following Coil treatment.
2. Any of the following during the immediate post-procedure period (3 days):

- Hemoptysis >200 ml, in 2 subjects at a single center.
- Respiratory failure requiring mechanical ventilation for >24 hours in 2 subjects at a single center.
- Pneumothorax requiring chest tube drainage for >7 days that occurs in 2 subjects at a single center, or greater than 4 of the first 20 subjects treated, regardless of center.

PneumRx shall notify FDA within 24 hours of stopping the study based on the stopping rules.

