With respect to safety, the Coil has been designed to be as safe as possible, which is supported by the fact that the Serious Adverse Event profile of the device is comparable to that reported in the literature for bronchoscopy alone in a sham procedure, specifically, referenced in the control patient population in the EASE trial (Shah, 2011), which observed 107 individuals for 6 months. Comparing the PneumRx OUS study results to the EASE sham control group, it appears that the risks associated with the Coil System are largely attributable to the bronchoscopic procedure itself rather than to the device per se. Specifically, the rate of serious events of pneumothorax, hemoptysis, COPD exacerbation and pneumonia are comparable between the LVRC treatment population and the EASE sham control group.

Table 5. Comparison of 6-Month SAE Data Per Procedure - LVRC System vs. EASE Sham Control

Reported SAE	PneumRx OUS studies (up to 6 Months)	EASE sham control (6 Months reported data)
Pneumothorax	14/238 procedures = 5.9%	1/107 procedures = 0.9%
Hemoptysis	1/238 procedures = 0.4%	0/107 procedures = 0%
Respiratory Failure	0/238 procedures = 0%	0/107 procedures = 0%
COPD exacerbation/ pneumonia ¹	41/238 procedures = 17.2%	18/107 procedures = 16.8%
Death	1*/238 procedures = 0.4%	4/107 procedures = 3.7%

* Not related to device or procedure

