2.3.2.1 Event Time Periods

In order to assess the safety profile of the LVRC without the interference of the procedure effect, adverse events and major complications will be summarized by time period. Each event will be included in the time period in which the event began, with the periods defined as follows:

- Peri-procedural: 0-30 days post each of the two treatment visits (visit 2 or visit 5)
- Between treatment #1 and visit 5: More than 30 days after visit 2, but prior to visit 5
- Between treatment #2 (or treatment #1 for subjects that miss Visit 5) and 6 months: More than 30 days after visit 5, but prior to 6 months post treatment #1

- Between 6 and 12 months: 6 or more months post treatment #1 through visit 10

Regarding the programming specifications for inclusion of AE records through the 12-month visit and each follow-up time period, please refer to Appendix 4.1 (item F).

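### The pneumothorax stopping rule does not say whether its 3-day window governs onset or the full criterion of more than 7 days' drainage; on the second reading it cannot be met.

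*Protocol*

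**What the plan says.** Protocol 8.1 (Study Stopping Rules) suspends treatment "if any of the following are observed". Rule 1 concerns deaths. Rule 2 puts three kinds of event under one time window: "Any of the following during the immediate post-procedure period (3 days".

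The third of these events is "Pneumothorax requiring chest tube drainage for >7 days that occurs in 2 subjects at a single center", with a second, study-wide limb of "greater than 4 of the first 20 subjects treated, regardless of center". The second is "Respiratory failure requiring mechanical ventilation for >24 hours in 2 subjects at a single center". The first is hemoptysis above a stated volume, also counted within a single center.

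Two other places bear on how the window might be read:

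- Protocol 7.1 lists pneumothorax with more than 7 days of drainage as a Major Complication. It measures the duration "from time of chest drainage tube insertion to the time of chest drainage tube removal" and attaches no 3-day window.
- SAP 2.3.2.1 assigns adverse events and major complications to reporting periods by start date: "Each event will be included in the time period in which the event began". It does not mention the stopping rules.

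**The concern.** The rule combines a 3-day window with a qualifying duration of more than 7 days and does not say how the two relate. The person applying it must decide whether a pneumothorax that starts on day 1 and is still draining on day 8 falls inside the window.

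The answer determines whether this trigger exists at all. The pneumothorax item is the only non-fatal stopping rule with a study-wide limb, since hemoptysis and respiratory failure count only within one center. Protocol 7.6 asks the DMC to recommend discontinuation according to these rules, so the committee needs one reading. The date also matters. Protocol 8.1 gives the sponsor 24 hours from stopping the study to notify FDA, so the moment at which a case counts has a regulatory consequence.

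**Working it through.** The documents give no operating characteristics for the stopping rules, so there is no stated figure to reproduce. The check is interval arithmetic on the rule's own numbers.

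**Inputs (Protocol 8.1):** window W = 3 days after the procedure, with the procedure on day 0; required duration D = more than 7 days of drainage; limbs of 2 subjects at one center, or more than 4 (at least 5) of the first 20 treated. For comparison, the ventilation item has D = more than 24 hours, that is 1 day.

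**Reading A: the whole criterion must be fulfilled inside the window.** This needs start day + D ≤ W, so the latest possible start is W − D.

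- Drainage: 3 − 7 = day −4, which is before the procedure. At most 3 days of drainage fit in the window, and 3/7 = 43% of the duration that must be exceeded. No subject can qualify, so neither limb can be met.
- Ventilation: 3 − 1 = day 2. The criterion can be met if ventilation starts before day 2.

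**Reading B: only onset must fall inside the window.** This needs start day ≤ 3, with the duration confirmed after start day + D. Assume the tube is placed on the day of onset.

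| Onset and tube | Confirmed after | Gap from close of window |
|---|---|---|
| Day 0 | 0 + 7 = day 7 | 7 − 3 = 4 days |
| Day 3 | 3 + 7 = day 10 | 10 − 3 = 7 days |

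A tube placed later than onset would move confirmation later still. The protocol does not say whether the case is dated to onset, to tube insertion or to confirmation. Nor does it say what applies to further treatments while a case is pending.

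**What the choice of reading does to the study-wide limb.** The documents give no rate of pneumothorax with onset within 3 days and more than 7 days of drainage, so the rate p per subject is assumed. With X ~ Binomial(20, p) and independent subjects, P(X ≥ 5) = Σ from k = 5 to 20 of C(20, k) pᵏ (1 − p)²⁰⁻ᵏ.

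| Assumed p | Reading A | Reading B |
|---|---|---|
| 2% | 0 | 0.00004 |
| 10% | 0 | 0.043 |
| 20% | 0 | 0.37 |

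These values only illustrate that the two readings separate as the true rate rises. They are not estimates for this study.

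**The case against.** The strongest reply is that Reading B is the natural one. In the bullet, the thing that occurs is the pneumothorax, and the drainage duration describes how severe it is. A pneumothorax that begins on day 1 and later proves to need 8 days of drainage did occur in the 3-day period. Nothing in Protocol 8.1 requires the drainage to end there. Reading A makes the sponsor's own rule impossible, which is a reason to doubt that it was intended. The only timing convention in the documents, in SAP 2.3.2.1, goes by start date.

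Most of this stands. A reader might infer that the rule can never be met, or that its two figures flatly contradict each other. The text does not support either statement: a limit on when an event starts is compatible with a threshold on how long it lasts. The reply still leaves a gap. The SAP convention covers summaries of adverse events and major complications only, the protocol nowhere adopts Reading B, and even Reading B has no counting date.

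A reader might also infer that the ventilation item has the same flaw. It does not: more than 24 hours fits within 3 days unless ventilation starts after about day 2.

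Nor does the Table 5 figure in Protocol 2.4, "14/238 procedures = 5.9" per cent, measure the problem. It is per procedure, runs up to 6 months and includes serious pneumothorax of any drainage duration. Set against 0.9% in the sham group, it shows only why a pneumothorax trigger deserves care.

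Finally, subjects do not depend on this item alone. Protocol 8.1 allows termination at any time on a DMC safety concern. Protocol 7.5 provides for DMC review of serious events as needed and of all adverse events quarterly. Protocol 7.1 requires serious events to be reported within one working day. These routes soften the consequence. They are discretionary, however, and do not replace a predefined suspension trigger.

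**Conclusion.** The point holds as an unresolved ambiguity in a safety trigger. If fulfilment within 3 days is required, both pneumothorax limbs are impossible to meet. If onset within 3 days is enough, both can be met, but a case is recognized only after day 7 to after day 10, and the protocol does not fix the date on which it counts. No passage in either document settles which reading applies.

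The zero probability belongs to the fulfilment reading alone and rests on nothing beyond the rule's own figures. The day 7 to day 10 range assumes that the procedure is day 0 and that the tube is placed on the day of onset. The frequency of qualifying events cannot be estimated from the documents, and it is not shown that sites, sponsor and DMC would in fact apply the rule differently. It should be corrected, chiefly because this is the only non-fatal rule with a study-wide limb.

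**What to change.** The sponsor and the DMC should reconcile the 3-day and the more-than-7-day figures in Protocol 8.1 so that the trigger is operable. The revised text should state:

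- what the 3-day window governs (onset of the pneumothorax or fulfilment of the criterion); and
- on which date a case is counted.

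Which reading is right is for the sponsor and the DMC to decide, and no threshold or clinical rule is proposed here. The cost is a sentence or two of clarifying wording, repeated in any operating document that the DMC uses. The clarification itself requires no change to endpoints, data collection or planned analyses.

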8.2 Insurance Coverage

If a device- or procedure-related incident occurs, the study Sponsor has a products liability insurance policy to cover damages within the legally prescribed scope.

9 Risks and Benefits

9.1 Potential Risks to the Subject

Participation in this clinical study may expose the subject to the following potential risks associated with the device and/or the procedure:

- **Bronchoscopy**

With any bronchoscopic procedure, there is the possibility of exacerbation of emphysema symptoms, fever, bleeding, laryngospasm, bronchospasm, irregular heartbeat, shortness of breath, infection, transient infiltrates, pneumonia (Djukanovic, 1998), pneumothorax (Bleeker, 1992), death or syncope. In the event that any of these were to occur, the subject will be treated for the condition. Some subjects may experience wheezing, coughing, or shortness of breath during the first few days following a bronchoscopy procedure. Of over 1300 LVRC procedures performed to date, there has been one reported death that was deemed related to the device or the procedure.

- **Infection including Pneumonia**

There is a risk of developing pneumonia as a result of the LVRC being placed in the airway, excess mucus production, or impairment of the ability of the lung to clear mucus and/or microorganisms from the airways. There is also an increased risk of infection in patients with emphysema over those who do not have emphysema (Zalacain, 1999).

- **Hemoptysis**

Hemoptysis is defined as coughing up blood > 5ml, which requires more than occasional blood-streaked sputum. There is also an increased risk of hemoptysis in patients with emphysema over those who do not have emphysema (Bidwell, 2005).

- **Moderate Sedation/Anesthesia**

There is a potential risk of developing side effects associated with the use of sedation and/or anesthesia. The risks of anesthesia depend on the agents

and/or gases used. The risks of anesthesia include respiratory acidosis and possible respiratory failure, postoperative pain, nausea and vomiting, dizziness, drowsiness, shivering, liver toxicity and/or cardiovascular events.

Trained professionals with extensive experience and expertise who routinely administer general anesthesia or local anesthesia with moderate sedation to subjects requiring multiple procedures will be responsible for the induction and associated monitoring required for this study. In addition, study subjects will be monitored throughout the recovery period as well after the recovery period, as indicated.

- **Coil Removal**

A Coil(s) may be removed up to 2 months following the treatment for medically indicated safety reasons (e.g., due to a persistent air leak or poor Coil location that may pose a safety risk). Other than during the LVRC treatment procedures (Study Visits 2 and 5), Coils should only be removed or repositioned for safety reasons, and Coils may not be replaced post-procedure. If the decision is made to remove a Coil(s), refer to the "Coil Removal Instructions" section in the Instructions for Use for details. The Investigator will notify the Sponsor of the need for removal prior to removing any Coil(s) and return the Coil(s) to PneumRx Quality Assurance for inspection.

In prior PneumRx OUS Feasibility Studies, numerous Coils have been bronchoscopically repositioned or removed during treatment procedures to improve placement or to deploy a different size Coil. All attempts to remove or reposition Coils during the over 200 procedures performed in the OUS studies have been successful and easy to perform as determined by the Investigator. There have been no reported complications or adverse events associated with the bronchoscopic removal or repositioning of the Coils during the LVRC procedures.

Coil(s) can and may be repositioned, replaced or removed during the treatment procedure (Study Visits 2 and 5). Coils can be removed bronchoscopically up to 2 months after the LVRC procedure, but only if medically indicated. Such medically indicated post-procedure removal would be considered a Major Complication, and will be recorded in the eCRF AE page. Although Coils have been removed as late as 4 months post-procedure in animal studies, the need to remove Coils in human trials is not anticipated based on safety data from European clinical trials. Note that the Coil removal procedure has not been tested after time periods longer than 4 months post-procedure.

- **Pneumothorax**

Pneumothorax is defined as the presence of air within the pleural space, which may or may not require chest tube insertion. There is also an increased risk of pneumothorax in patients with emphysema over those who do not have emphysema (Guo, 2005).

- **Reaction**

Reaction to the study device, including (1) an allergic reaction to the metal (nickel-titanium) that may require removal of the study device, and (2) an opacity on chest x-ray that may be difficult to differentiate from infectious pneumonia.

The following are potential risks that are associated with the tests required as part of the study conduct:

- **Blood draws**

The risks of blood draws include temporary pain and discomfort from the needle stick, and/or tenderness, redness or bruising at the site, bleeding, fainting and lightheadedness. While rare, there is a possibility of infection or a local blood clot.

- **Pulmonary function tests**

Pulmonary function tests are low risk procedures. They may occasionally cause dizziness and/or slight chest discomfort due to muscle soreness, but these are self-limited. There is a risk of fainting during forced exhalation.

- **Chest X-rays, CT Scans and Fluoroscopy**

Study subjects will have radiation exposure as a result of the chest X-rays, CT scans and fluoroscopy required as part of the protocol.

- **Medications required to perform bronchoscopy**

Drugs required for bronchoscopy could include lidocaine, atropine, narcotics, and one of the benzodiazepines. Although these drugs each have a number of potentially significant side effects, they are commonly used safely to perform bronchoscopy (Djukanovic, 1998).

Lidocaine toxicity has been described in association with bronchoscopy. At least one death has been reported in the literature as a result of lidocaine toxicity in a research Subject who underwent bronchoscopy (Clinical Trials Advisory Newsletter, 1996). Amounts of topical lidocaine given will be monitored and recorded and at all times will be less than 400 mg. Moderate sedation can be associated with respiratory suppression resulting in hypoxemia and the need for increased supplemental oxygen or the need for intubation with mechanical ventilation. In addition, moderate sedation can result in cardiovascular compromise with hypotension. To minimize these complications, sedation will be given in accordance with moderate sedation protocols applicable at the participating hospital and administered by trained professionals with experience in moderate sedation and ventilation.

Subjects with known sensitivity to drugs required to perform bronchoscopy are excluded from study participation. Should a subject experience a significant side effect for which there is concern, s/he will be managed as appropriate.

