1.2.2 Safety Endpoints

The primary safety analysis will tabulate subjects who experience one or more major complication(s) within 12 months post-baseline (and within defined blocks of time post-baseline). Major complications will be determined/adjudicated by the Clinical Events Committee.

Major Complications:

- Death;
- Pneumothorax that requires a chest drainage tube for more than 7 days (from time of chest drainage tube insertion to the time of chest drainage tube removal);
- Hemoptysis requiring blood transfusion(s), arterial embolization, or surgical/endoscopic procedure;
- COPD exacerbation that becomes life-threatening or disabling as a result of an increase in respiratory symptoms requiring in-patient hospitalization of >7 days with or without mechanical ventilation;
- Lower Respiratory Infections (including pneumonia) defined by new or increased clinical symptoms such as fever, chills, productive cough, chest pain, dyspnea and an infiltrate on plain chest x-ray and hospitalization for administration of intravenous antibiotics and/or steroids;
- Respiratory failure defined as a requirement for mechanical ventilatory support (whether via endotracheal tube or mask) for >24 hours; and
- An unanticipated bronchoscopy in order to remove one or more Coils due to a device-related AE. (Note: This definition does not include re-positioning, replacement or removal of the Coil(s) during the initial placement procedure.)

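### The Major Complication item names only later bronchoscopy to remove Coils, so a later bronchoscopy that only repositions one is left out of the primary safety count on a literal reading

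*Protocol*

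**What the plan says.** Protocol 9.1 (Coil Removal) limits what may be done to Coils once placement is over: "Other than during the LVRC treatment procedures (Study Visits 2 and 5), Coils should only be removed or repositioned for safety reasons". Replacement after the procedure is not allowed. The section gives examples of why a Coil might be removed later: "due to a persistent air leak or poor Coil location that may pose a safety risk". It then classifies the event: "Such medically indicated post-procedure removal would be considered a Major Complication, and will be recorded in the eCRF AE page". That sentence speaks of removal only.

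Protocol 7.1 lists the Major Complications. The item on re-intervention is "An unanticipated bronchoscopy in order to remove one or more Coils due to a device-related AE", with the Note "This definition does not include re-positioning, replacement or removal of the Coil(s) during the procedure". SAP 1.2.2 has the same item, but its Note ends differently: "This definition does not include re-positioning, replacement or removal of the Coil(s) during the initial placement procedure".

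The item feeds the main safety result. SAP 1.2.2 states: "The primary safety analysis will tabulate subjects who experience one or more major complication(s) within 12 months post-baseline".

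**The concern.** Poor Coil location is one of the protocol's own examples of a later safety problem, and moving the Coil is an evident alternative to taking it out. Two subjects could have the same device problem and each undergo an unplanned bronchoscopy, with the procedural and sedation risks set out in Protocol 9.1. The one whose Coil is removed is a Major Complication. The one whose Coil is moved is not, if the item is applied as worded. The classification would then follow the operator's choice, not what happened to the subject.

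At stake is whether the primary safety percentage covers all unplanned device re-interventions or only those ending in removal, and whether adjudicators would apply the item consistently.

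**Working it through.** There is no planned figure to reproduce. SAP 1.4 gives no sample size calculation, and neither document gives an expected Major Complication rate or a number of later repositionings. The check is a comparison of the texts, followed by a general expression for the size.

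**Classifying the possible cases**

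1. *Later unplanned bronchoscopy to remove a Coil for a device-related AE.* It counts under Protocol 7.1, Protocol 9.1 and SAP 1.2.2.
2. *Adjustment of a Coil during a placement procedure.* It is excluded by the Note in both documents. The protocol refers simply to the procedure and the SAP to the initial placement procedure. The SAP wording leaves open whether Visit 5 is meant as well as Visit 2.
3. *Later repositioning in a subject who also meets another component*, such as a chest tube for more than 7 days or hemoptysis treated endoscopically. The subject counts through that component.
4. *Later repositioning with no other component met.* Protocol 9.1 permits it for safety reasons, but no Major Complication item names it. The purpose stated in the item is removal. The Note does not add repositioning. Yet a Note that excludes repositioning during placement would be unnecessary if repositioning could never fall under the item, so an adjudicator could infer that later repositioning is in.
5. *Later removal for poor location before any AE has occurred.* Protocol 9.1 treats any medically indicated removal after the procedure as a Major Complication, whereas 7.1 and the SAP require a device-related AE. The same mismatch would affect a precautionary repositioning if only the word for repositioning were added to 7.1.

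Case 4 is the gap and case 5 is a neighbouring one. Adjudication does not clearly close either: Protocol 7.1 assigns it to the Medical Monitor and SAP 1.2.2 to the Clinical Events Committee, and neither document gives a rule for these cases.

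**Size**

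Let N be the number of subjects in the denominator, M the number with at least one Major Complication under the removal-only wording, and k the number with a later repositioning and no other Major Complication.

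- Rate under the removal-only wording: M/N
- Rate if later repositioning counts: (M + k)/N
- Difference: (M + k)/N − M/N = k/N

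Because k cannot be negative, the removal-only rate is equal to or below the wider rate. It is equal when k = 0. Neither k nor N is given, so no percentage can be stated.

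**Recovery from other tables**

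The underlying AE is recorded and tabulated (SAP 2.3.2.3). It may also be an SAE, for example under the criterion "requires intervention to prevent permanent impairment or damage". However, the tables are organised by MedDRA term, and the specified listing fields include none for an intervention. SAP 2.7 promises summaries of procedural and device data without naming a re-intervention count. The Protocol 9.1 instructions to notify the sponsor beforehand and to record the event as a Major Complication name removal only. A reader could see the adverse event without being able to count the repositionings.

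**The case against.** The strongest reply is that later repositioning is barely part of the plan. The Protocol 9.1 sentence is a restriction. Where the section says what can be done after placement, it speaks of removal: the two-month window, sponsor notification and the Major Complication statement all concern removal. The protocol does not anticipate even that being needed. This bears on frequency, and k may well be zero. It does not remove the permission in the text or supply a rule for a case that does occur.

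A second reply is that Major Complications are adjudicated, and the Note hints that later repositioning was meant to count. That stands as far as it goes: the text shows an ambiguity with a restrictive literal reading, not a settled exclusion.

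Third, some cases enter through the pneumothorax or hemoptysis components, the underlying AE is reported in any event, and Protocol 7.5 has the DMC review all adverse events quarterly. All of this stands. A reader might infer that such re-interventions vanish from safety reporting; the documents do not support that.

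Finally, how broad to make a composite is partly a design choice, and the study is descriptive, with no hypothesis or threshold resting on this item. That is a fair argument against simply widening the item, and a reason to keep the removal-only rate available beside the wider one.

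**Conclusion.** The point holds as a minor gap in definition. Protocol 9.1 allows Coils to be repositioned for safety reasons after the placement visits, while the Major Complication item names removal only. On the literal reading, a subject whose only qualifying event is a later repositioning bronchoscopy is not in the primary safety count. The Notes leave room for the opposite classification.

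The effect is k/N, of unknown size and possibly zero. If it is not zero, it can only lower the rate. This assumes that the item is applied as worded and that the subject meets no other component.

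A reader might go further and conclude that the safety rate is understated by some material number of percentage points. The documents give no frequency to support any such figure, and there is no understatement unless at least one such case occurs. No power or error rate is affected.

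**What to change.** Reconcile Protocol 7.1, Protocol 9.1 and SAP 1.2.2 as follows. This concerns what is counted, not when a Coil should be moved or removed.

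- Define the item as an unanticipated later bronchoscopy to remove or reposition one or more Coils because of a device-related AE or a device safety reason. The second ground aligns 7.1 and the SAP with 9.1 and covers precautionary cases.
- Keep the exclusion for adjustments made during either placement procedure, name Visits 2 and 5, and use the same Note in both documents.
- Record later repositioning on the AE eCRF in the same way as removal.
- Tabulate removal and repositioning on separate lines, and report the Major Complication rate with and without reposition-only cases, so that the removal-only definition stays available to anyone who needs it.

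The cost is a few words in each of the three places, one or two extra table lines, and possibly a slightly less favourable safety rate.
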